Milwaukee Day Cares Indoor Air Quality Assessment and Educational Response Study

Full study protocol and statistical analysis plan

August 11, 2018

Funded by the Clinical and Translational Science Institute of Southeastern Wisconsin
Award Numbers UL1TR001436, TL1TR001437, and KL2TR001438

Protocol Summary

Purpose

A research and community service partnership, comprising the Medical College of Wisconsin (MCW), UWM College of Nursing, and the non-profit asthma coalition Fight Asthma Milwaukee (FAM) Allies, proposes to describe and improve health-relevant indoor air quality (IAQ) conditions within diverse urban Milwaukee child day care environments. Inferior IAQ could contribute significantly to the development and exacerbation of asthma^{6,7,8} which affects 1 in 10 children in the State⁹. Day care IAQ has been assessed in few studies ^{1,10,11,12,13,14,15,16,17,18,19} and is largely unregulated by Wisconsin state law²⁰.

This project aims to understand the levels of indoor organic pollution and fine particles in the air, as well as temperature and humidity, using inexpensive, consumer-grade, Internet cloud- enabled continuous indoor air quality monitors. These air quality variables are established risk factors for both the development and exacerbation of asthma

Aims

1) Assess baseline IAQ characteristics in urban Milwaukee daycare settings.

- Objective 1.1: Deploy 36 IAQ monitors in 36 childcare settings by November, 2018.
- Objective 1.2: Collect 36 IAQ monitors from 36 daycare settings by February, 2019.
- Objective 1.3: Identify trends based on subtype analysis of IAQ baseline findings between large facility based, small home based and unlicensed daycare settings through data analysis by March 2019.

2) Determine the efficacy of the Green Cleaning for Asthma educational curriculum to alter IAQ and daycare staff cleaning/pest control behaviors objectively.

- Objective 2.1: Deliver Green Cleaning for Asthma classes for staff in 36 daycare organizations by January, 2019.
- Objective 2.2: Implement and collect IAQ pre and post surveys from 1 designated staff member in each of 36 daycare organizations by February, 2019.
- Objective 2.3: Identify trends in relationship to the educational intervention with regards to monitoring device variables including tVOC, PM2.5 and relative humidity variables and composites through data analysis by March 2019.
- Objective 2.4: Identify behavior changes of daycare staff with regards to cleaning practices, VOC generation as a result of the educational intervention through data analysis by March 2019.

3) Determine the feasibility of a future daycare oriented educational and research program to alter development of asthma and/or asthma exacerbations by improving IAQ.

- **Objective 3.1:** Assess the feasibility of educational training and community deployment of the educational curriculum.
- **Objective 3.2:** Develop proposals to investigate child health within daycare environments to determine future efficacy of IAQ interventions upon health outcomes such as asthma incidence, severity and exacerbations and daycare staff knowledge about asthma and recognition of symptoms of concern.

Research Design

A prospective randomized stepped-wedge trial is proposed. The partnership will engage day care facilities in a 4-month intervention. Half of the facilities will receive education at the second month, allowing the team to assess pre- and post-education air quality readings. The rest of the facilities will receive education at the third month. Devices will be removed from the day cares after the 4th month.

Enrolled day cares will be provided with IAQ monitoring and continuing education-eligible educational programs for day care staff. Nursing students from UWM, an Americorp worker, and MCW community health workers will be trained to provide the curriculum. The groups will be block randomized to start the educational program at either 1 month or 2 months after initial baseline IAQ measurements. Summaries of the findings from the assigned devices will be shared with day care staff at the conclusion of the study.

Two intervention schedules will be implemented:

Group A		Group B	
Month	Outreach	Month	Outreach
1	IAQ monitors deployed, pre survey	1	IAQ monitors deployed, pre survey
2	IAQ education delivered	2	
3		3	IAQ education delivered
4	IAQ monitors collected, post survey	4	IAQ monitors collected, post survey

Within each intervention group, two cohorts will be determined by licensure per the WI Dept of Children and Families' licensing for the program. Specifically, Licensed Family Child Care Centers provide care for up to eight children (to be referenced as home daycare), Licensed Group Child Care Centers provide care for nine or more children. Other data to be obtained from the daycare will include age of facility, type of heating, presence of air conditioning, type of air filtration, presence of gas ranges/stoves, usual cleaning regimen and cleaners, typical pesticide regimen, whether windows are typically opened, the State Youngstar rating (if a participant), # of children under 5, and over 5 years of age.

Procedures

Educational curriculum: A day care-specific modification of the FAM Allies “Green Cleaning for Asthma” curriculum will be provided to each facility by UWM nursing students, an AmeriCorps worker, FAM Allies volunteers, or MCW staff. Surveys of present cleaning/pesticide practices and air quality inventory will be obtained before and after the educational intervention. One person from each daycare will fill out the pre and post surveys and will receive a \$25 gift card upon completion of the post survey. Each daycare organization will receive a \$25 gift card for coordinating the training and housing the indoor air quality device.

IAQ monitoring: Portable IAQ devices will be deployed within the day care facility to measure variables pertinent to asthma such as total volatile organic compounds (tVOC), particulate matter (PM2.5), temperature, and relative humidity. These consumer-grade monitors are inexpensive, silent, unobtrusive, and upload data continuously via a cellular WiFi hotspot device provided by the study. Continuous data will be tagged with date of the educational intervention, and statistical analysis for trends over time as a result of the intervention will be conducted. Secondary analyses will evaluate which variables and practice changes are associated with improved IAQ.

Timeline providing details of each organization’s role:

April – May, 2018

- Public Allies (AmeriCorps) hiring process
- Flier development and marketing to day care organizations
- Recruitment of day care organizations
- Purchase supplies and contracts: IAQ monitors and hotspots

June, 2018

- FAM Allies volunteer training
- MCW staff training
- FAM Allies/MCW: Deploy 14 IAQ/hotspots in 14 day care organizations (Groups A and B)
- FAM Allies/MCW: Collect IAQ pre surveys from designated staff member in each of 14 day care organizations (Group A and B)

July, 2018

- FAM Allies/MCW: Teach educational intervention in 7 day care organizations (Group A)

August, 2018

- FAM Allies/MCW: Teach educational intervention in 7 day care organizations (Group B)

September, 2018

- FAM Allies/MCW: Collect 14 IAQ/hotspots from day care organizations (Groups A and B)

- FAM Allies/MCW: Collect IAQ post surveys from designated staff member in each of 14 day care organizations (Group A and B)
- FAM Allies/MCW: Compile data (Groups A and B)
- Public Allies (AmeriCorps) onboarding and training
- UWM nursing student training
- UWM Nursing: Deploy 6 IAQ/hotspots in 6 day care (Groups A2 and B2)
- UWM Nursing: Collect IAQ pre surveys from designated staff member in each of 6 day care organizations (Group A2 and B2)

October, 2018

- UWM Nursing: Teach educational intervention in 3 day care organizations (Group A2)
- Public Allies (AmeriCorps): Deploy 16 IAQ/hotspots in 16 day care organizations (Groups A3 and B3)
- Public Allies (AmeriCorps): Collect IAQ pre surveys from designated staff member in each of 14 day care organizations (Group A3 and B3)

November, 2018

- UWM Nursing: Teach educational intervention in 3 day care organizations (Group B2)
- Public Allies (AmeriCorps): Teach educational intervention in 8 day care organizations (Group A3)

December, 2018

- UWM Nursing: Collect 6 IAQ/hostpots from 6 day care organizations (Groups A2 and B2)
- UWM Nursing: Collect IAQ post surveys from designated staff member in each of 6 day care organizations (Group A2 and B2)
- UWM Nursing: Compile Data (Groups A2 and B2)
- Public Allies (AmeriCorps): Teach educational intervention in 8 day care organizations (Group B3)

January, 2019

- Public Allies (AmeriCorps): Collect 16 IAQ/hotspots from 16 day care organizations (Groups A3 & B3)
- Public Allies (AmeriCorps): Collect IAQ post surveys from designated staff member in each of 16 day care organizations (Group A3 and B3)
- Public Allies (AmeriCorps): Compile data (Groups A3 and B3)

February, 2019

Data compilation and submission to biostatisticians

March, 2019

- Final data reports and reporting to Funder
- Share data reports with all participating day care organizations

References

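### Aim 2 promises an objective assessment of staff behaviour, but behaviour is known only from unverified reports by the daycare, with no untaught comparison at the post survey

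*Combined protocol and SAP*

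**What the plan says.** - **Aims, Aim 2.** The curriculum's efficacy is to be judged by whether it can "alter IAQ and daycare staff cleaning/pest control behaviors objectively". The adverb covers air quality and behaviour together.
- **Aims, Objective 2.2.** The task is to "Implement and collect IAQ pre and post surveys from 1 designated staff member in each of 36 daycare organizations by February, 2019".
- **Aims, Objective 2.4.** The task is to "Identify behavior changes of daycare staff with regards to cleaning practices, VOC generation as a result of the educational intervention".
- **Procedures, Educational curriculum.** "Surveys of present cleaning/pesticide practices and air quality inventory will be obtained before and after the educational intervention". On who responds: "One person from each daycare will fill out the pre and post surveys".
- **Research Design, schedule table.** Groups A and B have the same survey entries: "IAQ monitors deployed, pre survey" in month 1 and "IAQ monitors collected, post survey" in month 4. Group A is taught in month 2 and Group B in month 3.
- **Research Design, paragraph after the table.** The daycare is also asked for its "usual cleaning regimen and cleaners, typical pesticide regimen", among other facility data. How this is collected is not stated.
- **Procedures, IAQ monitoring.** The devices record tVOC, PM2.5, temperature and relative humidity. Secondary analyses will relate changes in practice to better air quality.

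**The concern.** The plan claims for behaviour a property that its behaviour measure lacks. A respondent who knows that the daycare has been taught may give different answers in month 4 without any change in what staff do. The same person answers for all colleagues, so the measure is partly a proxy report. According to the timeline, the organisations that teach the classes also collect the post surveys from the same daycares, which may encourage favourable answers.

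Two conclusions are at stake. Under the present wording, a shift in reporting could be described as an objectively determined change in behaviour and credited to the class. Misreported practice would also enter the secondary analyses as an explanatory variable for air quality. The document is both protocol and SAP, and nothing else in it limits how behaviour results may be described.

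**Working it through.** The plan states no test, alpha, power or effect size for behaviour, so there is no figure to reproduce. The check compares the claim with the measurement and then with the schedule.

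**1. What is measured, and by whom**

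| Part of Aim 2 | Source described | Observed or verified independently of the daycare? |
|---|---|---|
| Air quality (tVOC, PM2.5, humidity, temperature) | Continuous monitor | Yes, by device |
| Cleaning practices | Survey by one person per daycare; regimen information from the daycare | None described |
| Pest control practices | Same | None described |
| Air quality inventory | Named alongside the surveys; who completes it is not stated | Not stated |

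No direct observation, purchase record, check by study staff or blinded rating of behaviour appears in the document.

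**2. Whether the randomised schedule supplies a comparison**

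| Month | Group A | Group B |
|---|---|---|
| 1 | Pre survey | Pre survey |
| 2 | Taught | Not yet taught |
| 3 | Already taught | Taught |
| 4 | Post survey | Post survey |

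The groups differ in taught status only between the two classes, and no survey is scheduled then. At the post survey they differ only in time since teaching: 4 − 2 = 2 months in Group A and 4 − 3 = 1 month in Group B. Comparing the groups on the survey would contrast earlier with later teaching, not taught with untaught. What remains is month 4 against month 1 within each daycare, which mixes any effect of the class with calendar time, repeated questioning and altered reporting. The monitors run throughout, so their data do cover the interval in which one group is taught and the other is not.

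**3. A hypothetical illustration**

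Assume one binary survey item, 36 complete pairs, an exact two-sided McNemar test and alpha 0.05; the documents give none of these except the 36 daycares. With b respondents switching to the taught answer, c switching back (c < b) and n = b + c:

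p = 2 × [C(n,0) + … + C(n,c)] × 0.5^n

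| b v c | Calculation | p |
|---|---|---|
| 6 v 0 | 2 × 1/64 | 0.031 |
| 6 v 1 | 2 × (1 + 7)/128 | 0.125 |
| 7 v 1 | 2 × (1 + 8)/256 | 0.070 |
| 8 v 1 | 2 × (1 + 9)/512 | 0.039 |

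Under these assumptions, six changed answers out of 36 (17%) would suffice if nobody switched back; with one reverse switch, eight would be needed. This shows how such a test behaves. It does not estimate the reporting bias in this trial.

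**4. Which daycares an added measure could still reach**

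The timeline deploys monitors in 14 daycares in June 2018, 6 in September and 16 in October: 14 + 6 + 16 = 36. The document is dated August 11, 2018. By its own schedule, 14 of 36 (39%) had passed the deployment visit and 6 + 16 = 22 had not.

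**The case against.** The strongest reply is that the adverb closes a sentence about two outcomes and is accurate for one of them. Objective 2.4 sets VOC generation beside cleaning practices, and VOCs are measured by device. The secondary analyses already plan to relate practice to monitor data. On this reading, the objective evidence on behaviour is the air itself.

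Part of this stands: the point must be confined to behaviour, and the plan does intend to use the two sources together. It does not make the behaviour measure objective. No rule says how practice is to be inferred from monitor data, and no monitor variable is named as a proxy for pest control.

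Several stronger readings are tempting, and the documents do not support them:

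- *The respondent was taught the preferred answers.* The classes are for staff, but the plan does not say that the designated person attends.
- *The inventory is certainly self-reported.* The sentence can also be read as naming two separate items, and it does not say who completes the inventory.
- *Behaviour is asked about only after the class.* The same person also completes a pre survey.
- *A false claim will be published.* The timeline mentions only reports to the funder and to the daycares.

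**Conclusion.** The point holds for the behaviour half of Aim 2 and for the causal wording of Objective 2.4. It does not touch the monitor outcomes. As described, the behaviour outcome is an uncontrolled before/after change in the reports of one person in each of 36 daycares. Calling it self-reported settles the first problem only; the missing untaught comparison would remain whoever did the reporting, so the attribution to the class has to go as well.

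The documents do not allow the size of any bias to be calculated. A reader might take the 6 v 0 result as showing that a spurious finding is likely, but it rests on an assumed test and alpha and on nobody switching back.

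The conclusion assumes that the document describes every behaviour measure. The survey form is not included, so its items could not be checked.

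**What to change.** 1. In Aim 2, attach the adverb to the monitor variables only.
2. In Aim 2 and Objective 2.4, restate the behaviour outcome as the before/after change in cleaning and pest control practices reported by one designated staff member per daycare, and remove the attribution to the class.
3. In Procedures, IAQ monitoring, label the practice changes used in the secondary analyses as self-reported.
4. Optionally, at the 22 daycares scheduled for deployment after this version, have the study staff who already visit record the products present at deployment and at collection. State that this record is unblinded and shows what is present, not what is used. By the timeline, a baseline record of this kind is no longer available for the 14 daycares deployed in June.

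A reader might want to require an accompanying tVOC change before any behaviour claim is made. That is not proposed: the plan links no pest control practice to tVOC, so such a rule could dismiss genuine change.

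Items 1 to 3 are edits with no extra visit or data, and by the timeline the first post surveys are not due until September 2018. Item 4 adds a short task to visits already planned. The downside is a more modest claim on behaviour.

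### Survey-reported cleaning and pest-control practices are measured only before anyone is educated and after everyone is, so the efficacy claim for them has no randomised comparison

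*Combined protocol and SAP*

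**What the plan says.** Research Design describes a randomised stepped-wedge trial in which day cares are block randomised to be taught one or two months after baseline measurement. The schedule table has the pre survey in month 1 for both groups, education in month 2 (Group A) or month 3 (Group B), and for both groups in month 4 "IAQ monitors collected, post survey".

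Procedures, under Educational curriculum, confirms the two occasions: "Surveys of present cleaning/pesticide practices and air quality inventory will be obtained before and after the educational intervention". The dated timeline repeats the pattern in all three deployment waves (surveys in June and September, September and December, October and January). Each survey entry covers the A and B groups of that wave together.

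The claims attached to these data are causal. Aim 2 is to "Determine the efficacy of the Green Cleaning for Asthma educational curriculum to alter IAQ and daycare staff cleaning/pest control behaviors objectively". Objective 2.4 is to "Identify behavior changes of daycare staff with regards to cleaning practices, VOC generation as a result of the educational intervention".

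The monitors work differently. They upload throughout the four months, and Procedures says "Continuous data will be tagged with date of the educational intervention".

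**The concern.** In this design the randomised information about education lies in the interval when Group A has been taught and Group B has not. The surveys are not taken in that interval. Any change from month 1 to month 4 therefore mixes the effect of the class with season, with being asked the same questions a second time, and with anything else that moved over those months.

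The result would be an uncontrolled before-after change. Because the study is presented as a randomised trial and Aim 2 puts staff behaviour beside air quality under one efficacy heading, a reader could easily give the survey result the standing of a randomised one.

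**Working it through.** **Inputs.** Group sizes and survey months come from the dated timeline, and education months from the schedule table and that timeline.

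| Wave | A | B | Pre survey | A taught | B taught | Post survey |
|---|---|---|---|---|---|---|
| 1 | 7 | 7 | Jun | Jul | Aug | Sep |
| 2 | 3 | 3 | Sep | Oct | Nov | Dec |
| 3 | 8 | 8 | Oct | Nov | Dec | Jan |

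A = 7+3+8 = 18 and B = 7+3+8 = 18, total 36, which matches the Aims. Post surveys are 14+6+16 = 36. Listed pre surveys are 14+6+14 = 34, because the October entry gives 14 for a wave of 16. That entry needs reconciling with Objective 2.2, but the number educated at the pre survey is 0 either way.

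**Educated sites once each month's classes are done.** Month 1: 0 of 36. Month 2: 18 of 36 (all of A, none of B). Months 3 and 4: 36 of 36. At both survey months the A-minus-B difference in exposure is zero.

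**Can the education effect be estimated from the two surveys?** It can only if adding an educated indicator raises the rank of the design matrix. With months 1 and 4 that indicator is identical to the month-4 indicator.

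| Model, 36 sites, months 1 and 4 | Rank without | Rank with |
|---|---|---|
| Day care + study month (36+1) | 37 | 37 |
| Day care + wave-by-month (36+3) | 39 | 39 |
| Day care + calendar month | 39 | 39 |
| Day care + sine/cosine season (36+2) | 38 | 39 |
| Day care + sine/cosine season + survey occasion | 39 | 39 |

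The calendar-month row covers the September overlap, where wave 1 is post and wave 2 is pre. It does not help once sites may differ: each wave supplies one change, and the calendar effects fit the three changes exactly. The sine/cosine row does identify a term, but only through an assumed curve and a non-randomised comparison between waves. The term is lost again once answering for the second time is allowed its own effect.

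**With one more survey in month 3, before Group B's class.** Wave-by-month or calendar-month effects give 42 without education and 43 with it (all waves), or 41 and 42 if only waves 2 and 3 are surveyed. The randomised comparison is 18 v 18, or 11 v 11 (3+8 per group).

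**Precision of that comparison.** ANCOVA on the pre survey and wave, continuous score in SD units, SE = √(2(1−r²)/n) with n per group; two-sided 5%, 80% power, noncentral t. The documents give neither a correlation r nor a survey score, so both are assumptions.

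- n = 18, df = 36−5 = 31, r = 0.5: SE = √(2×0.75/18) = 0.289; detectable difference 0.83 SD. For r = 0.7 to 0.3: 0.69 to 0.92 SD.
- n = 11, df = 22−4 = 18, r = 0.5: SE = √(2×0.75/11) = 0.369; detectable difference 1.09 SD. For r = 0.7 to 0.3: 0.90 to 1.21 SD.

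**The case against.** The strongest reply is that the plan hides nothing. It calls the surveys pre and post, links the staggered start to air-quality readings, and describes only an associational use of practice changes (which of them go with better air quality). On that view the fault is loose wording in Aim 2 and Objective 2.4, not a failed design. Much of this stands, and it is a good reason to put the rewording first. It does not remove the problem, because the two statements are causal as written.

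Other points and what remains of them:

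- Group A versus Group B in month 4 is a randomised comparison. It compares about two months with about one month since the class, not education with none, so it cannot show efficacy.
- Objective 2.4 lists VOC generation among behaviour changes. I read that part as measurable by the monitors' tVOC, which keeps a randomised window. If it is meant as a survey item, the concern covers it too.
- The detectable differences assume a continuous score and full follow-up. They do not carry over directly to yes/no practice items.
- A month-3 survey is more than a form. Three delivery teams would each have to run it in a matched window, and the respondent's $25 card is tied to the post survey only.

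None of these points supplies an educated versus not-yet-educated comparison for the surveys.

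**Conclusion.** The concern holds. For survey-reported cleaning and pest-control practices the plan supports a before-after change across 36 day cares (0 educated, then 36) and no randomised estimate of the effect of education. This follows from the schedule alone and does not depend on an assumed variance, correlation or effect size. It does not extend to monitor outcomes.

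The plan should be corrected on this point, because part of a stated efficacy aim has no randomised support. The detectable differences bear only on how useful an added survey would be, and they rest on the assumed correlation, a continuous score and complete follow-up.

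**What to change.** **Rewording, no cost.** State in Aim 2 and Objective 2.4 that survey-reported practice change is a descriptive pre-post finding. Limit the causal phrase to the monitor outcomes, including tVOC, and say whether VOC generation is read from the monitors or the survey.

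**Added survey, if the causal claim is to be kept.** Repeat the existing questionnaire once in both groups in month 3, before Group B's class, with the same respondent, mode and calendar window in A and B. Make A versus B at that survey, adjusted for the pre survey and wave, the analysis of survey-reported practices. Keep the month-4 survey as descriptive, noting that A versus B there compares time since education. State as a limitation that Group A answers after being taught the preferred practices, so self-report bias remains.

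The cost is 36 extra questionnaires, or 22 if only waves 2 and 3 are covered. The second figure may be the realistic one: the document is dated August 11, 2018, and wave 1 Group B is taught that month. Group A has no month-3 contact in the schedule table, so one must be added. Group B must be surveyed by the same mode, and not during the class visit if Group A answers remotely. The drawbacks are some respondent burden, coordination across teams and low precision.

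Either way, reconcile the 14 pre surveys listed for the 16-site third wave.

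### PM2.5 before-after readings, site-level improvement analyses and baseline type comparisons carry no outdoor or calendar-time reference, so outdoor change can be read as change or difference in the daycare

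*Combined protocol and SAP*

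**What the plan says.** All PM2.5 readings come from inside the facility (Procedures, IAQ monitoring): "Portable IAQ devices will be deployed within the day care facility to measure variables pertinent to asthma". PM2.5 is an outcome of the class under Objective 2.3: "Identify trends in relationship to the educational intervention with regards to monitoring device variables including tVOC, PM2.5 and relative humidity variables and composites". The same baseline readings serve Objective 1.3: "Identify trends based on subtype analysis of IAQ baseline findings between large facility based, small home based and unlicensed daycare settings".

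On the contrast, Research Design says: "Half of the facilities will receive education at the second month, allowing the team to assess pre- and post-education air quality readings". On the method, IAQ monitoring says only that "statistical analysis for trends over time as a result of the intervention will be conducted". Secondary analyses then relate practices to improved air.

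The design itself is randomised and stepped-wedge: "The groups will be block randomized to start the educational program at either 1 month or 2 months after initial baseline IAQ measurements". The Timeline runs it in three waves, deployed in June (14 sites), September (6) and October 2018 (16).

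No outdoor monitor, ambient record, season term or calendar-period term appears anywhere. The closest items are facility characteristics listed under Research Design: heating, air conditioning, filtration and "whether windows are typically opened".

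**The concern.** Indoor PM2.5 is part indoor generation and part outdoor air that has come in. The facility items bear on how much outdoor air enters. They do not say how much PM2.5 was outside on a given day.

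Both groups move from untaught to taught as the calendar advances. Any outdoor change over a wave therefore points the same way at all of its sites, and enrolling more sites in that wave does not average it out of a before-after reading. Three consequences follow for the analyses as written:

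- A before-after PM2.5 change can be credited to the class when the outdoor air moved.
- A site can be classed as improved because outdoor air cleared while it was monitored. Device summaries go back to the daycares, so the misreading would reach them.
- Daycare types can appear to differ at baseline because they were enrolled in different months. Licensure cohorts are described within each intervention group, but nothing fixes the mix of types by wave.

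**Working it through.** The documents give no PM2.5 SD, target effect, power calculation or infiltration figure, so there is no planned figure to reproduce. The site count does agree: 14 + 6 + 16 = 36, with 7 + 3 + 8 = 18 sites in each group.

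**From the plan:** three waves of four months; Group A taught in month 2, Group B in month 3.

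**Assumed:** daily outdoor PM2.5 SD 5 ug/m3; lag-1 correlation 0.5; 28 days per month; share entering F = 0.3 to 0.8; between-site SD of that share 0.2.

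**1. Random outdoor variation, before-after.**
- SD of a monthly mean: 5 × sqrt(((1 + 0.5)/(1 − 0.5))/28) = 5 × sqrt(3/28) = 1.64.
- Difference of two independent months: 5 × sqrt(6/28) = 2.31.
- Indoors: 0.3 × 2.31 = 0.69 to 0.8 × 2.31 = 1.85 ug/m3.
- Using all scheduled months gives the same order. Group A (1 month against 3): 1.64 × sqrt(1 + 1/3) = 1.89, indoors 0.57 to 1.51. Group B (2 against 2): 1.64 × sqrt(1/2 + 1/2) = 1.64, indoors 0.49 to 1.31.

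**2. Steady outdoor drift of g per month, before-after.** Group A: mean of months 2-4 minus month 1 = 3 − 1 = 2 months. Group B: 3.5 − 1.5 = 2 months. The false change is 2 × g × F.

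**3. Simulation of the plan's schedule.** 36 sites, no true effect, 400 runs per row. Further assumptions: between-site SD 3, monthly residual SD 1.5. The second analysis uses site effects plus wave-by-month effects.

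| Outdoor scenario | Mean before-after change | False positives, before-after | False positives, within wave and month |
|---|---|---|---|
| F 0.3, g 0.5 | 0.32 | 21% | 5% |
| F 0.5, g 1 | 0.99 | 94% | 4% |
| F 0.8, g 2 | 3.21 | 100% | 6% |
| F 0.5, random citywide monthly SD 1 | −0.02 (SD 0.37) | 12% | 6% |
| F 0.5, random citywide monthly SD 2 | 0.01 (SD 0.61) | 30% | 5% |

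With no outdoor change, before-after was sound (false positives 4-6%, SE about 0.27). The monthly SD of 1.64 from step 1 lies between the last two rows. The within-wave analysis had bias of about 0 throughout, with an SE of about 0.6.

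**4. What is left after the within-wave comparison.**
- Unequal entry between sites: 0.2 × 2.31 = 0.46 ug/m3 per site.
- Pooled, 18 against 18: 0.46 × sqrt(2/18) = 0.15. Added to an SE of 0.60: sqrt(0.60² + 0.15²) = 0.62, about 3% more.
- Second wave alone, 3 against 3: 0.46 × sqrt(2/3) = 0.38.
- Unmeasured site-specific outdoor variation (SD 0 to 3, F 0.5) raised the simulated SE from 0.60 to 0.84 without bias.

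**5. Objective 1.3.** Suppose two daycare types differ by 20 to 40 points in the share of their sites in a given wave, and outdoor PM2.5 differs by 2 to 4 ug/m3 between waves. At F = 0.5 the false type difference is 0.5 × 0.2 × 2 = 0.2 to 0.5 × 0.4 × 4 = 0.8 ug/m3.

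**The case against.** The strongest reply is that this is a randomised stepped-wedge trial. In month 2 Group A has been taught and Group B has not, so an outdoor shift shared within a wave cancels in a same-month comparison with no outdoor data at all. That is right, and step 3 confirms it. A reader might infer that the randomised education effect is itself biased by 0.7-1.9 ug/m3. The documents do not support that: the figure belongs to an uncontrolled before-after contrast. But the safeguard is available rather than planned, since no written analysis compares the groups within a month. It also does not reach Objective 1.3 or the improved-air analyses.

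The reply also holds that an outdoor covariate adds little once time is modelled. This largely stands. A single city record takes one value per date, so period effects absorb much of it, and the gain on the pooled estimate is small (step 4). A regional monitor cannot measure the site-specific variation behind the larger rise in SE.

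It might also be inferred that the class cannot alter the outdoor contribution, so any adjustment is free of bias. The curriculum's content is not described, and an air quality inventory is repeated after the class, so an effect on ventilation cannot be excluded. Outdoor concentration is safe to adjust for. Window-opening recorded after the class is not, because it may lie on the causal path.

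Lastly, total indoor PM2.5 is what children breathe and is a valid outcome. Describing it needs no outdoor reference; attributing its change to the class, or a difference to the type of daycare, does.

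**Conclusion.** The concern holds in a limited form. The before-after contrast, the improved-air analyses and the Objective 1.3 comparison, as written, are open to confounding by outdoor PM2.5 and calendar time. On the assumed inputs the before-after shift is about 0.7-1.9 ug/m3 (1 SD, one month against one month), before any seasonal drift. A baseline type difference of 0.2-0.8 ug/m3 could arise from enrolment timing alone. For the randomised effect, the remedy for bias is the within-wave comparison; outdoor data then mainly improve precision, modestly.

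Every magnitude rests on assumed variability, drift, infiltration and type mix. With no planned effect size or SD in the documents, these figures show the mechanism and a range and cannot be set against a target effect. The change is worth making because the text as written permits the misattribution and the remedy is cheap.

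**What to change.** In Procedures, IAQ monitoring, specify:

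- The PM2.5 education effect is estimated with site effects and wave-by-calendar-period effects, so that Groups A and B are compared within the same wave and period.
- Each site-day is linked to a routine Milwaukee outdoor PM2.5 record (assumed available), entered as a time-varying covariate. If its slope is allowed to vary by site, only window-opening and filtration recorded before the class are used.
- The same outdoor covariate enters the Objective 1.3 and improved-air analyses.
- Total indoor PM2.5 is still reported, unadjusted, as the description of exposure.

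The cost is a merge by date and a few model terms. No new measurement is needed at any daycare, and the merge can be done when data go to the biostatisticians in February 2019. There are two limits. A regional monitor only approximates outdoor air at each site. The within-wave comparison is also less precise than before-after appears to be (SE about 0.6 against 0.27 in the simulation), because both groups are taught from month 3 and the concurrent contrast rests on about one month per wave.
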